10.7 ECOG

The frequency counts and percentages of subjects for each ECOG performance status scale will be presented for baseline and worst-case post-baseline. A shift table from baseline to the worst-case post-baseline will be generated as well.

ECOG performance status data will be listed for each subject.

10.8 Subsequent Anti-Cancer Therapy

Subsequent Anti-Cancer Therapy data status data will be listed for each subject

11 PRO FROM THE EORTC QLQ-C30 ANALYSES

Analyses of EORTC QLQ-C30 data will use the Safety Population and be by treatment arm. No missing items or forms will be imputed.

11.1 Missing Data

Patterns of missing EORTC QLQ-C30 data will be summarized descriptively using the following categories: no missing measurements, no baseline measurement, no post-baseline measurement, 1 missing post-baseline measurement, 2 missing post-baseline measurements, 3 missing post-baseline measurements, and 4+ missing post-baseline measurements. These categories are mutually exclusive and collectively exhaustive; that is, every subjects will be in one and only one category for this summary. Subjects will be assigned to a category using the order given; that is, a subject with 1 possible QoL measurement that is missing will be in the no post-baseline category, not the 1 missing post-baseline measurement category. For each category, the number and percentage of subjects in each category will be calculated. The denominator to use for percentages is the number of subjects in the safety population for each treatment arm.

11.2 Scoring the EORTC QLQ-C30 Results

Scoring of all scales will use the EORTC QLQ-C30 Scoring Manual instructions for version 3.0 of the QLQ-C30 instrument.

Let I_i be the score for the i th item on the QLQ-C3 instrument, $i=1, 2, 3, \dots, 30$, ranges be the difference between the possible maximum and the minimum response to individual items for scale s , and n_s be the number of items on the scale s .

For all scales, the *RawScore*, RS_s , is the mean of the component items:

$$RawScore_s = RS_s = (I_1 + I_2 + \dots + I_{n_s}) \div n_s$$

Then for **Functional scales**:

$$Score_s = \{1 - (RS_s - 1) \div range_s\} \times 100$$

and for **Symptom scales/items** and the **Global health status /QoL**: $Score_s = \{(RS_s - 1) \div range_s\} \times 100$.

Global health status / QoL	Scale	Number of Items	Range	Version 3.0 Item Numbers
Global health status/QoL	QL2	2	6	29, 30
Functional scales				
Physical functioning	PF2	5	3	1 to 5
Role functioning	RF2	2	3	6, 7
Emotional functioning	EF	4	3	21 to 24
Cognitive functioning	CF	2	3	20, 25
Social functioning	SF	2	3	26, 27
Symptom scales / items				
Fatigue	FA	3	3	10, 12, 18
Nausea and vomiting	NV	2	3	14, 15
Pain	PA	2	3	9, 19
Dyspnoea	DY	1	3	8
Insomnia	SL	1	3	11
Appetite loss	AP	1	3	13
Constipation	CO	1	3	16
Diarrhoea	DI	1	3	17
Financial difficulties	FI	1	3	28

* Item range is the difference between the possible maximum and the minimum response to individual items; most items take values from 1 to 4, giving range = 3.

11.3 Summary of EORTC QLQ-C30 Results

EORTC QLQ-C30 scores for each scale and single-item measure will be summarized by baseline and all scheduled visits using the total number of subjects with a measurement on that

scale at that visit, the mean, standard error, median, minimum, and maximum. These summaries will also report change from baseline using the same descriptive statistics. Box and whisker plots of change from baseline for each scale by visit will also be produced.

11.4 Analysis of Change from Baseline

For each of the EORTC QLQ-C30 multi-item scales and single-item measures, a mixed model for repeated measures will be run.

For one analysis, the best overall response for a subject will be dichotomized into 2 levels: response of CR or PR, and response of SD, PD, or NE. Another analysis will use a different dichotomization: response of CR, PR, or SD, and response of PD or NE.

The SAS procedure call is

```
Proc mixed data=<SAS dataset name>;
  class visit response subject;
  model <scale name> = visit response visit*response / htype= 1,3;
  repeated subject;
  lsmeans visit*response / diff;
run;
```

Only differences in least square means between each post-baseline visit and the baseline visit will be reported. The dataset structure will have a separate record for each subject, visit, scale or single-item measure, and score.

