2.3 Exploratory Objectives

The exploratory objectives of Phase 1 and 2 are to assess patient reported quality of life outcomes, pre- and post-treatment blood biomarkers, pre- and post-treatment tumor biopsies for immunological assessment, and explore any potential association between these biomarker measures and antitumor activity. In addition, anti-IMO-2125, anti-ipilimumab, and anti-pembrolizumab antibody formation will be assessed.

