	14.2.3.1b	Overall Survival (OS) (PIIEE and SIIIE Populations)
	14.2.3.2.1a	Progression-Free Survival (PFS) – RECIST v1.1 (PIIEE and/or PPIEE Populations)
	14.2.3.2.1b	Progression-Free Survival (PFS) – RECIST v1.1 (PIIEE and SIIIE Populations)
	14.2.3.2.2a	Progression-Free Survival (PFS) – irRECIST (PIIEE and/or PPIEE Populations)
	14.2.3.2.2b	Progression-Free Survival (PFS) – irRECIST (PIIEE and SIIIE Populations)
	14.2.3.3.1a	Duration of Response (DOR) – RECIST v1.1 (PIIEE and/or PPIEE Populations)
	14.2.3.3.1b	Duration of Response (DOR) – RECIST v1.1 (PIIEE and SIIIE Population)
	14.2.3.3.2a	Duration of Response (DOR) – irRECIST (PIIEE and/or PPIEE Populations)
	14.2.3.3.2b	Duration of Response (DOR) – irRECIST (PIIEE and SIIIE Population)
14.2.4		Measurable Disease Assessment
	14.2.4.1.2	Change from Baseline in the Sum of the Longest Diameters (PIIEE and/or PPIEE Populations)
14.2.5		Patient Reported Outcomes – Quality of Life
	14.2.5.1	Missing EORTC QLQ-C30 Responses
	14.2.5.2	EORTC QLQ-C30 Scores by Scale
	14.2.5.3	EORTC QLQ-C30 Change from Baseline –Response vs. Non-Response
	14.2.5.4	EORTC QLQ-C30 Change from Baseline –Disease Control vs. Disease Progression or Not Evaluable

List of Figures

Phase 1

ICH Heading	Table Number	Table Description
	14.3.1	Box plot of Complement testing by visit (Safety Population)
	14.3.2	A scatterplot of the baseline and worst-case on-treatment QTcF (Safety Population)

Phase 2

ICH Heading	Table Number	Table Description
	14.2.1	Waterfall Plot of Maximum Changes from Baseline in the Measurable Tumor Burden (PIIEE and PPIEE Populations)
	14.2.2	Overall Survival (PIIEE and PPIEE Populations)
	14.2.3.1	PFS - RECIST v1.1 (PIIEE and PPIEE Populations)
	14.2.3.2	PFS - irRECIST (PIIEE and PPIEE Populations)
	14.3.1.1	Box plot of Complement testing by Treatment arm (Safety Population)
	14.3.2.1	A scatterplot of the baseline and worst-case on-treatment QTcF (Safety Population)

List of Data Listings (Phase 1 and Phase 2)

ICH Heading	Listing Number	Listing Description	CRF page(s)
16.2		SUBJECT DATA LISTINGS	
16.2.1		Discontinued Subjects	
	16.2.1.1	Subject Disposition	Study Exit Status, Derived
16.2.2		Protocol Deviations	
	16.2.2.1	Protocol Deviations	Derived
	16.2.2.2	Inclusion/Exclusion Criteria	Inclusion/Exclusion Findings
16.2.4		Demographic Data	
	16.2.4.1	Demographics	Demographics
	16.2.4.2.1	Medical History	Medical History
	16.2.4.2.2	Melanoma Characteristics	Melanoma Characteristics

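### Section 11.4 promises a repeated-measures model for the QLQ-C30, but its PROC MIXED call does not model correlation between a subject's visits

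*SAP*

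**What the plan says.** SAP Section 11.4 states that for every QLQ-C30 scale and single item "a mixed model for repeated measures will be run", and then gives the procedure call.

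- The classification line is "class visit response subject". The fixed effects are visit, response and their interaction.
- The covariance part consists only of "repeated subject".
- On the data: "The dataset structure will have a separate record for each subject, visit, scale or single-item measure, and score". Each subject level therefore recurs, once per visit.
- On the output: "Only differences in least square means between each post-baseline visit and the baseline visit will be reported".
- On missing data, Section 11 adds: "No missing items or forms will be imputed".

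The results go to Table 14.2.5.3 ("EORTC QLQ-C30 Change from Baseline –Response vs. Non-Response") and its companion for disease control, Table 14.2.5.4. Section 2.3 makes quality of life an exploratory objective, but Section 8.2 keeps the QLQ-C30 analyses within the scope of the SAP.

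**The concern.** The text and the code of one section disagree. A repeated-measures model must say which records belong together and how they are correlated. Here subject is named as the repeated effect, visit is absent from that statement, and no option defines a block of correlated records. Subject is not a fixed effect either. No other section supplies a covariance structure for this model.

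The call is given as the specification, so it governs 30 models per arm: the 15 scales or items listed in Section 11.2, each with two response dichotomies. If it fails to run, the covariance structure will be chosen after the data are in. If it runs with independent errors, two things follow:

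1. **Precision.** Each reported difference compares the same subjects at two visits, but its standard error ignores the pairing.
2. **Dropout.** Each difference compares the subjects still observed in a response group with that whole group at baseline. Nothing is imputed, so the model is the only step that could adjust for selective dropout, and with independent errors it does not.

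**Working it through.** The SAP gives no figure for this model to reproduce, and no correlation, standard deviation or dropout rate for the QLQ-C30. Every numerical input below is therefore an assumption, and the results are conditional on the call running with independent errors.

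**Reading the call.** There are two possible behaviours.

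- *Diagonal residual matrix:* all records are independent and no within-subject correlation is estimated.
- *Records sharing a repeated level get identical rows:* for 40 subjects with 4 visits the residual matrix is 160 × 160 with rank 40. It is singular and the fit stops.

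Neither is a repeated-measures model.

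**Standard error, complete data.** Let σ be the score SD, n the subjects in the response group and ρ the correlation between two visits (compound symmetry).

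- Independence: SE = σ√(2/n)
- Correct: SE = σ√(2(1−ρ)/n)
- Ratio = 1/√(1−ρ)
- Actual two-sided size at nominal 5% = 2[1 − Φ(1.96/√(1−ρ))]

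For power, take σ = 20, n = 28 non-responders (with 12 responders) and a true 10-point change. At ρ = 0.5:

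- Independence SE = 20√(2/28) = 5.35, so rejection needs a difference above 1.96 × 5.35 = 10.48.
- The true SE is 20√(1/28) = 3.78, so power ≈ 1 − Φ((10.48 − 10)/3.78) ≈ 45%.
- With correlation modelled, power ≈ Φ(10/3.78 − 1.96) ≈ 75%.

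The power columns below are from 10,000 simulated trials and agree with this approximation. The first two columns are from the formulas.

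| ρ | SE ratio | Actual size | Power, independence | Power, correlation modelled |
|---|---|---|---|---|
| 0.3 | 1.20 | 1.9% | 45% | 60% |
| 0.5 | 1.41 | 0.6% | 44% | 74% |
| 0.7 | 1.83 | 0.03% | 43% | 93% |

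A separate fit to 300 simulated data sets (40 subjects, 5 visits, ρ = 0.5, unit variance) gave the same picture. The contrast's empirical SD was 0.192. The independence model reported a mean SE of 0.276 with size 0.3%; a random-intercept model reported 0.195 with size 4.7%.

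**Bias under dropout, no true change.** Assumptions: baseline plus Weeks 8, 17 and 29; contrast at Week 29 in the 28 non-responders; monotone logistic dropout; 3,000 trials per scenario; higher score is better. Responders had 5% random dropout per visit.

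Completely random dropout gives a bias within 0.2 of zero. When dropout depends on the last observed score, at ρ = 0.5:

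| Odds ratio of dropout per SD worse | Bias, 10% dropout per visit | Bias, 25% dropout per visit | Rejection at 25% |
|---|---|---|---|
| 1.6 | +1.3 | +3.3 | 4.3% |
| 2.7 | +2.6 | +5.8 | 8.0% |
| 4.5 | +3.1 | +7.0 | 12.8% |

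With 10% dropout per visit, rejection is 1.5% to 3.1%. Over ρ from 0.3 to 0.7 the bias ranges from +0.9 to +8.9 points. An unstructured repeated-measures model stays within 0.2 of zero in all these cases. Repeat simulations of the independence fit agreed to within about 0.3 points.

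If dropout depends instead on the unseen current score (ρ = 0.5), the independence fit gives +1.8 to +9.2 and the correct model still gives +1.0 to +5.9.

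A positive bias means apparent improvement for the functional and global scales. Under the Section 11.2 scoring, higher symptom scores are worse, so there the same effect has a negative sign.

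**The case against.** The strongest reply accepts the coding slip and disputes its weight.

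- **The call may simply stop.** A failure would be seen in programming, and Section 5 provides independent validation and senior statistical review. This stands in part: the figures above apply only if the call runs. But the same review checks consistency with the plan, and the plan is this call. A late repair would leave the covariance structure chosen after the data are in.
- **Section 11.3 also reports change from baseline by visit,** a paired summary with its own standard error, and Section 11.1 tabulates missing-data patterns. This limits the harm. It does not handle dropout: the summary describes only subjects still observed, and in the same simulations at ρ = 0.5 it was itself biased by about −0.5 to −2.2 points.
- **No decision rests on these tables.** Section 11 states no hypothesis, target difference or success rule, so size and power at two-sided 5% are illustrations. This stands.
- **The larger biases need heavy, selective dropout.** At 25% per visit about 28 × 0.75³ ≈ 12 of 28 subjects remain, and the 28/12 split matches no planned arm. PRO collection also continues into follow-up and ends at progression, which best response partly captures; dropout explained by response group alone causes no bias. This also stands, and is why the figures are given as a range.

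**Conclusion.** The point holds: the call in Section 11.4 does not fit the model that the section names, and nothing elsewhere in the SAP corrects it. That rests on the text alone and is true whichever way the software treats the call.

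The size of the effect is conditional. With independent errors and complete data the error is conservative: standard errors are too large by 1.20 to 1.83 for ρ from 0.3 to 0.7, with a corresponding loss of power. With dropout driven by earlier scores the reported changes look too favourable, by about 1 to 9 points over the assumed range. There is no such bias if dropout is completely random or explained by response group alone. A correct model removes the bias under missing-at-random dropout and only part of it otherwise.

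The reach is limited to the exploratory QLQ-C30 models. It should be corrected, but it does not threaten the trial's main conclusions.

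**What to change.** Replace the REPEATED statement so that visit is the repeated effect and subject defines the block, for example `repeated visit / subject=subject type=un;`. State a fallback in advance, such as `type=cs`, because an unstructured matrix may not converge in a small arm. State a denominator-degrees-of-freedom method on the MODEL statement, for example `ddfm=kr`. Another stated within-subject structure, such as a random subject effect, would also satisfy the text. Keep the same least-squares-mean contrasts within response group.

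The cost is one or two lines of SAP code before database lock. The data collection and table list do not change.

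### The QLQ-C30 tables titled as comparisons of response groups would show two within-group changes, with no standard error, confidence interval or visit-specific test of their difference

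*SAP*

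**What the plan says.** SAP Section 11.4 runs a repeated-measures mixed model for every QLQ-C30 scale and single item. Best overall response is first "dichotomized into 2 levels: response of CR or PR, and response of SD, PD, or NE". A second run regroups it: "Another analysis will use a different dichotomization: response of CR, PR, or SD, and response of PD or NE".

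The code is "model <scale name> = visit response visit*response / htype= 1,3", followed by "lsmeans visit*response / diff". It has no ESTIMATE or CONTRAST statement. The closing reporting rule is "Only differences in least square means between each post-baseline visit and the baseline visit will be reported".

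Appendix E lists the two resulting tables as "EORTC QLQ-C30 Change from Baseline –Response vs. Non-Response" (14.2.5.3) and "EORTC QLQ-C30 Change from Baseline –Disease Control vs. Disease Progression or Not Evaluable" (14.2.5.4).

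Elsewhere, Section 11 sets the PRO analyses by treatment arm, and Section 11.3 adds descriptive summaries of scores and changes by visit without mentioning a split by response group. Table shells are in a separate document (Appendix F) that is not at hand.

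**The concern.** The table titles pose a question about two groups: does quality of life change differently in responders and non-responders, or in patients with and without disease control? The model contains the term that addresses it, visit*response. The reporting rule then keeps only each group's movement from its own baseline.

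A reader of a table with a *vs.* title will compare the two columns anyway. If one column's change is clearly different from zero and the other's is not, the natural inference is that response is associated with quality of life. That inference is unsafe, because two separate within-group results are not a test of their difference. The pattern can recur over the 15 scales and items in Section 11.2 and at every post-baseline visit.

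This is separate from the model's covariance specification. Correcting that would change the standard errors, but the contrast would still be missing.

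**Working it through.** The SAP gives no sample size, alpha or power for the PRO models, so there is no figure of its own to reproduce. The check has three parts.

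**1. What the code produces.** Write the cell means as m(g,v), with g = R or N (the two response groups) and v = 0 for baseline. The target at visit v is

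D(v) = [m(R,v) − m(R,0)] − [m(N,v) − m(N,0)].

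It has four non-zero coefficients. Each difference from the DIFF option has two (one cell minus another), so D(v) cannot be among them. Counting the pairs for 2 groups and V visits (V is an assumption, because the PRO row of the schedule is broken in the text):

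| Type of difference | Formula | V = 4 | V = 5 |
|---|---|---|---|
| Within group, post-baseline vs baseline (reported) | 2(V − 1) | 6 | 8 |
| Between groups, same visit | V | 4 | 5 |
| One group's post-baseline vs the other's baseline | 2(V − 1) | 6 | 8 |
| Other pairs | remainder | 12 | 24 |
| All pairs | 2V(2V − 1)/2 | 28 | 45 |
| D(v) found among them | – | 0 of 3 | 0 of 4 |

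The same-visit group differences are computed, but the reporting rule excludes them. They also ignore any baseline difference between the groups.

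**2. Why two within-group results do not replace D(v).** Assume changes of +10 and +4, each with standard error 4, in independent groups.

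- Group R: z = 10/4 = 2.5, p = 0.012.
- Group N: z = 4/4 = 1.0, p = 0.317.
- Difference: 10 − 4 = 6; SE = √(4² + 4²) = 5.66; z = 6/5.66 = 1.06, p = 0.289.

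One group is significant, the other is not, and the data say little about whether they differ.

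**3. How often the columns would disagree when the true changes are equal.** Assumptions, none of them from the SAP: the same true change δ in both groups, SD of change 20, separate paired t-tests at two-sided 5%. Power comes from the noncentral t with n − 1 degrees of freedom and noncentrality δ√n/20. With powers a and b, exactly one group is significant with probability a(1 − b) + b(1 − a).

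| n (R / N) | δ | Power R | Power N | Exactly one significant |
|---|---|---|---|---|
| 8 / 24 | 10 | 0.232 | 0.650 | 0.232 × 0.350 + 0.650 × 0.768 = 0.58 |
| 16 / 16 | 10 | 0.465 | 0.465 | 2 × 0.465 × 0.535 = 0.50 |
| 7 / 14 | 8 | 0.146 | 0.284 | 0.35 |
| 8 / 24 | 12 | 0.312 | 0.804 | 0.61 |
| 7 / 30 | 12 | 0.268 | 0.888 | 0.68 |

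At the same total of 32 and δ = 10, moving from 16/16 to 8/24 raises the probability from 0.50 to 0.58. Most of it is therefore present with balanced groups. The cause is moderate power in each group, and imbalance adds to it. Over these settings the range is 0.35 to 0.68.

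**The case against.** **The model already tests the comparison.** The htype option requests Type 1 and Type 3 tests of visit*response, which ask whether the pattern over visits differs between groups. The reporting rule can be read as selecting among least-squares-mean differences without suppressing those tests. This stands in part, and a reader who infers that the SAP has no test of the comparison goes too far. But the SAP does not clearly say that the test will be reported, and an omnibus F-test gives no size, direction or visit.

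**The difference can be had by subtraction.** True. It would be wrong to say that the comparison cannot be estimated at all from these tables. What is missing is its standard error, confidence interval and visit-specific test.

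**No significance claim is planned.** Section 11.4 mentions no p-value or alpha for the PRO analyses, and the shells are not at hand. The two-sided 5% above is this review's assumption. It illustrates a likely misreading and is not a planned decision rule.

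**Unequal groups are the cause.** A reader might infer this from the 58% figure. The 50% at equal sizes shows otherwise. For the disease-control split, nothing in the SAP shows that either group would be much larger.

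**No objective asks for this contrast.** Section 2.3 lists assessment of quality of life; the association with antitumor activity that it names is for biomarkers. Reporting within-group change only is a permissible exploratory choice, but then the *vs.* titles do not describe the content. Appendix E allows minor index changes without a SAP amendment, so retitling is easy.

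**The contrast could be over-read.** This stands. Best overall response is determined after baseline, so a responder-minus-non-responder difference describes an association and is not an effect of response.

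**Conclusion.** The point holds as a mismatch within the SAP. Two tables titled as comparisons of response groups would show each group's change from its own baseline, and neither the code nor the reporting rule supplies the precision or a visit-specific test of the difference between them.

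The documents do not support the stronger conclusion that the tables can say nothing about the comparison: an interaction test is requested and the point difference follows by subtraction.

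The discordance figures (58% at 8/24, 50% at 16/16, and 35% to 68% over the settings shown) rest on assumed group sizes, SD, true change and test level. They use separate t-tests in place of the pooled mixed model, so they show the order of magnitude only. The consequence is confined to the interpretation of an exploratory endpoint; the primary ORR analysis is not affected. This is a minor but worthwhile improvement.

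**What to change.** In Section 11.4, amend the reporting sentence and add one ESTIMATE per post-baseline visit for D(v), the between-group difference in change from baseline, with a 95% CI. Then, in Tables 14.2.5.3 and 14.2.5.4:

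- show D(v) and its CI in an added column;
- keep the within-group changes, with the number of subjects contributing to each visit-by-response cell;
- report the visit*response test;
- footnote the comparison as exploratory and non-causal, because the groups are defined by an outcome determined after baseline.

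If no comparison is intended, retitle both tables as within-group change by response category and leave the reporting rule as it is.

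The cost is a few lines of code and one table column, or two title changes. No new data are needed.
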